7 VISIT SCHEDULE AND STUDY ASSESSMENTS

7.1 Study visits

The study visits and their respective time windows are listed in [Table 5](#) and [Table 6](#).

In the event of premature discontinuation of study treatment, the EOT visit must take place as soon as possible and no later than 7 days after the last dose of study treatment. In such case, all assessments planned at the Month 6 visit must be performed at the EOT visit. Subjects who prematurely discontinue study treatment for any reason will not be replaced.

An exit interview will be conducted by telephone as soon as possible after the end of the study treatment phase (or EOT visit), ideally within 2 weeks in English-speaking subjects at US and Canadian sites.

Safety follow-up information will be collected during the FU1 visit (all subjects) and FU2 visit (only in fertile males) via telephone call. At the FU1 visit, safety follow-up information includes use of concomitant therapy, AE/SAEs, result of pregnancy test, and reporting of pregnancy (as needed) in female subjects or male subjects’ female partners. Fertile male subjects will be reminded to continue using contraception until at least 3 months following EOT. At the FU2 visit, safety follow-up information includes reporting of pregnancy (as needed) in male subjects’ female partners.

For subjects followed in the PTOp, safety follow-up information may also be collected during a site visit if it coincides with the originally scheduled visits.

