### 9.2.3 Change from baseline to Month 6 in plasma Gb3 (ng/mL)

Plasma Gb3 data will not be available for statistical analysis until the study database is locked and the randomization code is broken.

The values collected during the study will be mapped to protocol visits according to the windowed times described in [Table 5](#).

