**Table 5 Time windows for visit re-mapping**

Visit	Study day (nominal value)	Lower limit study day	Upper limit study day
Baseline	1	Day of screening visit	1
Month 1	30	2	45
Month 2	61	46	75
Month 3	91	76	106
Month 4	122	107	136
Month 5	152	137	167
Month 6	183	168	213

Should more than one value fall within the same time window, then the closest value to the planned study day will be assigned to the visit. If the values are equidistant to the planned study day, the latest value will be retained.

Using the plasma Gb3 data collected at baseline and Month 6, the change from baseline to Month 6 will be calculated as the difference (Month 6 – baseline) and also as the percent change from baseline ( $100 \times [\text{Month 6} - \text{baseline}] / \text{baseline}$ ).

Values reported as below the limit of quantification (BLQ) will be set to the limit of quantification in the analyses. The number of values reported as BLQ by treatment group and visit will be included in the tables.

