### 15.3.3 Change from baseline to Month 6 in plasma Gb3

This absolute change endpoint will be analyzed using the mFAS. All available data will be used regardless of occurrence of ICEs such as premature treatment discontinuation or changes in background medication.

Missing data will be imputed applying an MI approach assuming MAR similarly to that described in Section 15.2.4.1. The imputation model includes the baseline value, the two stratification factors (sex and ERT treatment status at screening), Month 1, Month 3, Month 5, and Month 6 values and treatment group.

Subjects with the baseline value missing will be excluded from this analysis.

The MI procedure will be implemented by the following SAS® code:

```
proc mi data=h nimpute=500 seed=32767 min=. . . . 0 0 0 0 minmaxiter=1000000out=h2;  
  mcmc impute = monotone;  
  var treatment sex ertstatus baseline y1 y3 y5 y6;  
run;  
proc mi data=h2 nimpute=1 seed=32767 min=. . . . 0 0 0 0 minmaxiter=1000000out=h3;  
  by _imputation_;  
  class treatment sex ertstatus;  
  var treatment sex ertstatus baseline y1 y3 y5 y6;  
  monotone regression;  
run;
```

The MAR assumption can be considered reasonable for this endpoint as it is an objective assessment and not patient-reported and therefore less likely to be related to reasons for study withdrawal. In addition, patients, physicians as well as the sponsor are blinded to the plasma Gb3 results until after database lock and a lower amount of missing data is expected compared to the abdominal pain and stool consistency endpoints.

The analysis, within each imputed dataset, will be performed using an ANCOVA as described in Section 15.2.3.

Results from these analyses are combined using Rubin's methodology [Rubin 1987] implemented in SAS® PROC MIANALYZE.

The mean difference in changes from baseline to Month 6 between lucerastat and placebo together with its two-sided 95% CI and p-value will be reported.

To explore the robustness of inferences from the main analysis described above to deviations from its underlying assumptions regarding the nature of missing data, control-based MI assuming MNAR using the CR and J2R approaches [described in Sections 15.2.3 and 15.2.4.2] will be applied.

Subgroup analyses will be performed similarly to those described in Section 15.2.6 by including the respective subgroup and subgroup by treatment interaction in the ANCOVA.

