#### 15.4.1.2 Change from baseline to Month 6 in UACR

The ANCOVA after MI assuming MAR described in Section 15.3.3 will be used to analyze the change from baseline to Month 6 on the mFAS, on original values at baseline, Month 1, Month 3, Month 5, and Month 6.

Subjects with the baseline UACR value missing will be excluded from this analysis.

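### SAP Table 5 sends some plasma Gb3 and UACR samples to Months 2 and 4, which the imputation model does not contain, so they drop out of the MI/ANCOVA; the effect on the Gb3 test is probably small and cheap to remove

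*SAP*

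**What the plan says.** - **Mapping.** SAP 9.2.3 states for plasma Gb3: "The values collected during the study will be mapped to protocol visits according to the windowed times described in" SAP Table 5, titled "Time windows for visit re-mapping". SAP 9.3.2 (UACR) and SAP 13 (other biomarkers) apply the same table. Two of its rows, giving nominal day, lower limit and upper limit, read "Month 2 61 46 75" and "Month 4 122 107 136". If several values share a window, the one nearest the nominal day is kept. No rule moves a value to a neighbouring window.
- **Sampling.** Protocol 3.1.1 makes Months 2 and 4 telephone visits. The protocol's visit schedule (Protocol Table 5) places biomarker and laboratory sampling at site visits only.
- **Model.** The Gb3 imputation in SAP 15.3.3 uses "Month 1, Month 3, Month 5, and Month 6 values and treatment group", and its code lists `y1 y3 y5 y6`. SAP 15.4.1.2 analyses UACR "on original values at baseline, Month 1, Month 3, Month 5, and Month 6". SAP 19 analyses the other biomarkers as in 15.3.3.
- **Premature discontinuation.** Protocol 7.1 requires an EOT visit within 7 days of the last dose, at which "all assessments planned at the Month 6 visit must be performed at the EOT visit". The subject is then followed at the originally scheduled visits up to Month 6.
- **Data use.** SAP 15.3.3 also says "All available data will be used regardless of occurrence of ICEs".

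**The concern.** The windows cover six monthly visits, while sampling and model terms cover four. A mandatory EOT sample can fall on any study day. If it falls in the Month 2 or Month 4 window, it is labelled with a visit that the model does not hold.

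Gb3 is the second hypothesis in the fixed sequence. For a subject who stops treatment and then leaves the study, the EOT sample may be the last Gb3 value available. The imputation of Month 6 would then rest on an older value although a later one was measured. The MAR assumption in SAP 15.3.3 conditions on what was observed, so leaving out an observed value weakens it.

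The gap carries into the copy-reference sensitivity analysis, the log-scale repeat (same imputed data) and the other biomarkers. UACR has one further source of loss: Protocol 7.2.4.2.2 collects urine at unscheduled visits too. Biomarkers are not sampled at unscheduled visits (Protocol 7.1.2).

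**Working it through.** **1. How SAP Table 5 was built.** Nominal days are 30, 61, 91, 122, 152 and 183. Midpoints of neighbouring pairs are 45.5, 76, 106.5, 137 and 167.5. These reproduce the table's limits (45/46, 75/76, 106/107, 136/137, 167/168). It is a plain six-visit midpoint table, not adapted to measures sampled at four visits.

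**2. Share of days affected.** Month 2: 75 - 46 + 1 = 30 days. Month 4: 136 - 107 + 1 = 30 days. Days 2 to 167, before the Month 6 window opens: 166 days. Share: 60/166 = 36.1%.

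**3. Scheduled visits.** The protocol windows for sampled visits are Days 21-38, 84-98, 145-159 and 169-197. Every day in them maps to the correct visit. To be stranded, a visit must be well outside its window:

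| Visit | Stranded when | Days outside protocol window |
|---|---|---|
| Month 1, late | from Day 46 | 46 - 38 = 8 |
| Month 3, early | Day 75 or before | 84 - 75 = 9 |
| Month 3, late | from Day 107 | 107 - 98 = 9 |
| Month 5, early | Day 136 or before | 145 - 136 = 9 |

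**4. Premature-EOT samples.** The documents give no discontinuation rate. Assume 5-20% of the 118 randomized subjects (SAP 2) stop early, with EOT days uniform over Days 2-167:

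- 118 x 0.05 x 60/166 = 2.1
- 118 x 0.20 x 60/166 = 8.5

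**5. Those that matter to the test.** The endpoint is Month 6 minus baseline. If Month 6 is observed, including in the post-treatment observation period, the stranded value does not enter that subject's change. If half of the affected subjects lack Month 6 (assumed), 1.1 to 4.3 subjects remain. With a quarter to all lacking it, the range is 0.5 (2.1 x 0.25) to 8.5.

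**6. Information lost per such subject.** Assume equal correlation r between all visits. Residual variance of Month 6 is 1 - r² given baseline alone, and 1 - 2r²/(1 + r) given baseline and the EOT value. At r = 0.3 the ratio is 0.910/0.862 = 1.06; at r = 0.9 it is 0.190/0.147 = 1.29. This is the case of a subject with no other post-baseline value. With a Month 1 value as well, the loss is smaller: at r = 0.5 the variances are 1 - 0.5/1.5 = 0.667 and 1 - 0.75/2 = 0.625, a ratio of 1.07 against 0.750/0.667 = 1.13 without it.

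**7. Does redrawing the windows suffice?** Midpoints of the four sampled visits are (30 + 91)/2 = 60.5, (91 + 152)/2 = 121.5 and (152 + 183)/2 = 167.5. No day is then mapped outside the model, but only one value per window is kept. After an on-time Month 1 visit (at most 9 days from Day 30), an EOT value on Days 46-60 lies 16-30 days from Day 30 and is discarded. The same holds for Days 107-121 after an on-time Month 3 visit (at most 7 days from Day 91, against 16-30). Only Days 61-75 and 122-136, 15 + 15 = 30 of the 60 days, are rescued for subjects who attended on schedule.

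**The case against.** The strongest reply is that little is lost. On-schedule visits are never affected, and subjects who stop early are followed with sampling to Month 6. That stands, and it limits the point to a few subjects.

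A reader might infer that the plan breaks its own promise in "All available data will be used regardless of occurrence of ICEs". In context that sentence expresses the treatment-policy strategy: data are not excluded because of discontinuation or other medication. It does not promise that every off-schedule sample becomes a predictor in the imputation. The mismatch sits awkwardly with it, but the case rests on the windows and model terms, not on that sentence.

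A second reply is that the sensitivity analyses already cover this. That holds only in part. The jump-to-reference code in SAP 15.2.4.2, applied to Gb3, imputes Month 6 from sex, ERT status and baseline, so its final step does not use the intermediate values. The main and copy-reference analyses do use them.

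A third reply is that wider windows mix stages of response. The protocol's Phase 1b figures show mean plasma Gb3 changes of -39% at Week 4 and -55% at Week 12. This is a real cost, but it arises almost only where the slot would otherwise be empty, and a mistimed value still informs the imputation more than none.

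**Conclusion.** The mismatch is in the text, and following the plan as written leaves some measured Gb3, other biomarker and UACR values out of the MI/ANCOVA. Left out here means absent from that analysis. By-visit summaries may still show the values, and SAP 15.3.3 does not say whether the Gb3 MMRM would include them.

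Under the assumptions in the working, about 2-9 premature-EOT samples are stranded, and fewer matter to the Month 6 test. A reader might infer that ordinary visit delays cost data, or that the Gb3 test is biased. The documents support neither: in-window visits map correctly, and nothing here shows a bias or a changed test result. An EOT sample is taken within a week of the last dose, so restoring it mainly sharpens the imputation; it does not correct for stopping treatment. UACR lies outside the test sequence. The eGFR slope uses actual dates and is not affected. This is a worthwhile correction of modest effect.

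**What to change.** Before database lock, while Gb3 is still blinded, add a second window table for measures taken only at site visits and refer to it in SAP 9.2.3, 9.3.2 and 13:

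| Visit | Study days |
|---|---|
| Month 1 | 2-60 |
| Month 3 | 61-121 |
| Month 5 | 122-167 |
| Month 6 | 168-213 |

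Keep the nearest-to-nominal-day rule and add one sentence: if a premature-EOT value is not retained in its own window and the next modelled visit before Month 6 has no value, it fills that visit (Days 46-60 to Month 3, Days 107-121 to Month 5). Without this sentence, half of the affected days stay lost for subjects who attended on schedule.

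Model terms and code do not change. Adding Months 2 and 4 to the model instead is not workable, because almost every subject would be missing them.

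The cost is one table and one sentence. A few values will sit further from their nominal day, where the slot would otherwise be empty. The one exception is a Month 1 value on Day 14 or earlier (30 - 16 = 14), which a value from Day 46 onward could replace if it is at least as close to Day 30. In-window visits are untouched, because the newly admitted values are at least 16 days from the nominal day.

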## 15.4 Analysis of other efficacy variables

### 15.4.1 Renal function endpoints

#### 15.4.1.1 Subject eGFR slope from baseline to Month 6

A linear mixed model will be used to analyze this endpoint on the mFAS. The outcome variable will be the observed eGFR values measured from baseline up to the last available visit in the treatment period or PTOP. The following fixed effects will be included in the model: the two stratification factors (sex and ERT treatment status at screening), time (as a continuous variable), treatment group, and the treatment group by time interaction.

The model will include a random intercept and a random slope. An unstructured covariance structure will be used for estimation of correlation between random intercept and random slope. If this model fails to converge, a diagonal covariance structure will be used.

Time is derived as (eGFR measurement date – randomization date) \* 12 / 365.25. Time will be set to 0 for the baseline value. The eGFR slope will be reported as mL/min/1.73m^2 per month.

The individual subject eGFR slopes will be derived as the random slope of each subject added to the mean slope in the respective treatment group.

Subjects with only one non-missing eGFR value from baseline up to Month 6 will not be included in the model and their eGFR slope will therefore be missing.

To assess the treatment effect, the estimate and the two-sided 95% CI will be calculated for the difference in the mean eGFR slope between lucerastat and placebo.

This analysis will be implemented by the following SAS® code:

```
proc mixed method=reml;
  class subjid sex ertstatus treatment;
  model egfr = sex ertstatus time treatment treatment*time / ddfm=kr solution cl;
  random intercept time / sub=subjid type=un gcorr solution group=treatment;
  ods output solutionf = fixed;
  ods output solutionr = random;
  estimate 'Lucerastat' time 1 treatment*time 1 0 / cl;
  estimate 'Placebo' time 1 treatment*time 0 1 / cl;
run;
```

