6.1.4 Other efficacy endpoints

6.1.4.1 Renal function endpoints

- Subject eGFR slope from baseline to Month 6;
- Changes from baseline to Month 6 in urine albumin-to-creatinine ratio (UACR).

Of note, long-term outcome of lucerastat on renal function parameters will be further assessed in the OLE study (separate protocol).

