- Cerebrovascular (transient ischemic attacks, ischemic stroke, white matter lesions, other)
- Bones (osteoporosis, osteopenia, other)
- Skin (angiokeratoma, anhydrosis, hypohydrosis, hyperhydrosis, acanthosis, hyperkeratosis, skin peeling, other)
- History of ERT infusion reaction
- eGFR slope before screening (derived from historical serum creatinine values)

Additional information from the site about detail of  $\alpha$ -GalA activity, and GLA gene mutation (c., p.) and transcript (NM\_), will be reported in the listing only.

Incident case information will be derived as yes, no, not known when APMH.MHOCCUR = Y, N, U, respectively.

Historical serum creatinine values will be used to derive corresponding past eGFR values according to the CKD-EPI formula [see protocol section 7.2.4.2.1]. Serum creatinine values in SI units (LB.LBSTRESN) will be converted to mg/dL by dividing by 88.4 without rounding and eGFR results will be rounded to the nearest integer value. For each serum creatinine value, the age at time of collection will be used to derive the corresponding eGFR. The age at time of collection will be derived from the age at screening as  $DM.AGE - \text{floor}[(\text{date screening} - \text{date sample})/365.25 + 0.5]$ , assuming that, on the average, the (unknown) birth date is 6 months before the screening date. The subject historical eGFR slope (mL/min/1.73 m^2 per year) will be estimated via a linear mixed model as described in Section 15.4.1.1 but only including time as a fixed effect, using all eGFR values up to and including the randomization visit (i.e., including values collected during the study). Subjects with eGFR values at screening and/or randomization but without any historical eGFR values will not be included in the mixed model and their historical eGFR slope will therefore be missing.

Any calculation involving a “Time since” a date of interest is defined as  $(\text{Date of randomization} - \text{Date})$  in days / 365.25. In the event of incomplete date of interest with missing day, “Time since” is calculated as  $[(\text{year of randomization} - \text{year of Date}) + (\text{month of randomization} - \text{month of Date})/12]$ . In the event of incomplete date of interest with missing day and month, “Time since” is calculated as  $(\text{year of randomization} - \text{year of Date})$ .

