### 9.3 Renal function endpoints

#### 9.3.1 Subject eGFR slope from baseline to Month 6

Using all eGFR values from baseline to Month 6, the subject eGFR slope (mL/min/1.73 m^2 per year) will be estimated via a linear mixed model, as described in Section 15.4.1.1.

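### The SAP gives the eGFR slope per year in Sections 7.4 and 9.3.1 but models and reports it per month in Section 15.4.1.1, with no conversion between the two

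*SAP*

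**What the plan says.** Three SAP sections bear on the unit.

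- **SAP 9.3.1, the on-study endpoint.** The slope is expressed in mL/min/1.73 m² "per year) will be estimated via a linear mixed model, as described in Section 15.4.1.1".
- **SAP 7.4, the historical slope.** The slope has the same unit, "per year) will be estimated via a linear mixed model as described in Section 15.4.1.1 but only including time as a fixed effect". The section changes the data, the fixed effects and the exclusion rule relative to 15.4.1.1. It does not define a time variable for the slope.
- **SAP 15.4.1.1, the model both cite.** Time is the number of days from the "randomization date) \* 12 / 365.25. Time will be set to 0 for the baseline value". The reporting sentence reads "The eGFR slope will be reported as mL/min/1.73m 2 per month". The printed code takes the arm slopes with a coefficient of 1 on time: "estimate 'Lucerastat' time 1 treatment*time 1 0 / cl".

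Protocol 6.1.4.1 names the endpoint, "Subject eGFR slope from baseline to Month 6", without a unit. SAP 14.9 says the historical slope is summarized as a quantitative variable and gives no unit or conversion. SAP Section 20 lists only subgroup changes.

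**The concern.** For the on-study slope, 9.3.1 and 15.4.1.1 give one endpoint two units. A single reported value cannot meet both, and the SAP does not say which section prevails.

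The historical slope can go three ways:

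1. The programmer rescales time to years, and the value is right.
2. The programmer carries over the per-month label, and the value is right but contradicts 7.4.
3. The programmer runs the 15.4.1.1 model with its month-based time and puts the output under the unit in 7.4. The value is then 12-fold too small. This is the literal reading of 7.4.

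The third outcome would be easy to miss, because a small negative slope looks like near-stable renal function. Even if 7.4 and 15.4.1.1 are each followed correctly in their own unit, the same report would carry historical and on-study slopes on scales that differ by a factor of 12.

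**Working it through.** **Inputs**

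- Time formula: days × 12 / 365.25 (SAP 15.4.1.1).
- Nominal study days 30, 91, 152 and 183 for Months 1, 3, 5 and 6 (SAP Table 5).
- Historical creatinine from up to 2 years before screening (Protocol 7.2.1.1), and screening from Day −49 at the earliest (Protocol Table 5).
- The documents give no expected slope, so the slopes used below are assumptions for illustration.

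**Step 1: the unit of the time variable**

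| Day | Days × 12 / 365.25 | Days / 365.25 | Ratio |
|---|---|---|---|
| 30 | 0.986 | 0.082 | 12.000 |
| 91 | 2.990 | 0.249 | 12.000 |
| 152 | 4.994 | 0.416 | 12.000 |
| 183 | 6.012 | 0.501 | 12.000 |

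The model's time is in months: 365.25 days gives 12.00. The earliest historical value would sit at about −(2 × 365.25 + 49) = −779.5 days, which is −25.6 on the month scale and −2.13 in years.

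**Step 2: whether anything converts the output**

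The ESTIMATE statements have a coefficient of 1 on time and no multiplier or divisor, so they return slopes per month. Individual slopes are the random slope plus the arm's mean slope, also without rescaling. None of 7.4, 9.3.1, 14.9 and 15.4.1.1 contains a step that multiplies by 12. Within 15.4.1.1 the formula, the code and the reporting sentence agree, so its results are correct per month.

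**Step 3: the size of the error if unconverted output is labelled per year**

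Slope per month = slope per year / 12.

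| Assumed slope per year | Model output (per month) |
|---|---|
| −1 | −1/12 = −0.083 |
| −3 | −3/12 = −0.250 |
| −5 | −5/12 = −0.417 |

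With 7.4 and 15.4.1.1 each kept in its own unit, a subject declining steadily at 3 per year would show −3.00 (historical) and −0.25 (on study).

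**Step 4: whether inference changes**

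If months = 12 × years, then slope per year = 12 × slope per month, and its standard error scales by the same 12. The test statistic is unchanged. In the random-slope model the slope variance scales by 144 and the intercept–slope covariance by 12, so the fitted model is the same.

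A numerical illustration agrees. It used 118 simulated subjects at days 0, 30, 91, 152 and 183, with assumed slopes of −2 (lucerastat) and −3 (placebo) per year. Subject intercepts were fitted by least squares.

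| | Month scale | Year scale |
|---|---|---|
| Placebo slope | −0.2818 | −3.3822 |
| Treatment difference | 0.1247 | 1.4960 |
| 95% CI for the difference | 0.0481 to 0.2012 | 0.5777 to 2.4144 |
| p-value | 0.0015 | 0.0015 |

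**The case against.** The strongest reply is that only one direct contradiction exists. The per-month sentence stands under the on-study heading, so it governs that endpoint, and a programmer coding from 15.4.1.1 would label the output correctly. SAP 7.4 describes a separate fit and states its own unit. Its reference to 15.4.1.1 can be read as borrowing the model structure only. The same section measures its time-since variables in years, as a difference "in days / 365.25. In the event of incomplete date of interest with missing day", which suggests years were intended. On this reading no number in the SAP is wrong. Correctly labelled slopes in different units are not an error, and no comparison of historical with on-study slope is planned. A mislabelled on-study slope might also be noticed, because observed eGFR and its change from baseline are tabulated by visit (SAP 10.2 and 16.2.1).

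Part of this stands. The 12-fold error is conditional, 15.4.1.1 is internally sound, and the stakes are modest. The numerical illustration is not the planned PROC MIXED model, so the unchanged test rests on the scaling argument.

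The reply does not remove the conflict between 9.3.1 and 15.4.1.1. For 7.4, the year-based rule is written only for the time-since variables. The section names what it changes in the borrowed model, and the time variable is not among the changes. The by-visit tables start from the treatment baseline, so they give no check on the historical slope.

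**Conclusion.** The concern holds. The unit conflict for the on-study slope is unconditional. The numerical error is conditional: a factor of exactly 12 if 15.4.1.1 output goes unconverted under the per-year unit of 7.4 or 9.3.1, and zero if the per-month label is kept or time is rescaled. The factor follows from the time formula alone and does not depend on the assumed slopes.

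The consequence is limited to reported values and labels. The on-study slope is an other efficacy endpoint outside the four-hypothesis sequence in SAP 15.1, and the historical slope is descriptive. Tests and p-values do not change, provided the same model converges on either scale. The point should be corrected, but it does not threaten the trial's main conclusions.

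**What to change.** Adopt one of these options and apply it to all three sections.

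- **(a) Years throughout.** In 15.4.1.1 define time as (measurement date − randomization date) / 365.25 and change the reporting sentence to per year. SAP 7.4 and 9.3.1 stay as written. Cost: two sentences and the line that derives time. The printed PROC MIXED code is unchanged.
- **(b) Months throughout.** Leave 15.4.1.1 alone and relabel 7.4 and 9.3.1 as per month, with no multiplication by 12. Cost: one unit label in each section and no code change.
- **(c) Model in months, report in years.** Multiply slopes, standard errors and confidence limits by 12 for reporting, for both the on-study and the historical slope, and change the 15.4.1.1 reporting sentence to per year. Cost: one sentence and one reporting step.

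Option (a) is the simplest, because the whole correction sits in one section. The options must not be mixed: relabelling per month and also multiplying by 12 would create a new 12-fold error. None of them affects data collection or any test.
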